## 11.8 Maintenance of Trial Treatment Randomization Codes

Randomization will occur at the end of each baseline study visit. Randomization codes will be determined by a block randomization strategy at each site. Sealed envelopes will contain a study identification number on the outside and the randomization arm on the inside. Study staff will chose randomization envelopes sequentially and only open the card after enrollment, survey and specimen collection has occurred. There will be a separate staff member who will create and number the envelopes thereby shielding clinic study staff from knowing the randomization scheme. No study staff at the clinic will have access to the randomization database or numbering scheme. Every six months, a randomization interim analysis will be performed by Tulane staff for DSMB review to ensure that the randomization strategy is successful. The randomization arm will be noted on the study file and in the participant's data once the baseline visit is completed. No laboratory or clinical staff will have access to the randomization database.

## 11.9 Participant Enrollment and Follow-Up

Women will be enrolled from three public clinics in New Orleans, LA (CrescentCare Health and Wellness, Birmingham, AL (JCDH STD Specialty Clinic) and Jackson, MS (Crossroads Clinic). Each will continue to enroll up until two months from study end to allow sufficient time for follow up; therefore anticipated enrollment duration will be 30 months. The clinics' census is adequate to achieve sample size.

Version: 11.0

Version date: 1/2/17

### **11.10 Planned Interim Analyses**

The DSMB will be responsible for monitoring all aspects of the study, including those that require access to blinded data, and will follow the procedures detailed in the DSMB charter. The Data Coordinating Center (DCC) representative will be responsible for preparing and presenting up-to-date statistical reports on the progress of the study at semiannual meetings. These reports will include data on recruitment, randomization, adherence, adverse drug responses, as well as statistical tests and special analyses requested by the DSMB. During the active recruitment phase, the DSMB will monitor the progress of recruitment and the random allocation of participants to the various treatment arms and may recommend modifications in (or termination of) the trial if the study design goals are not being met.

### **11.11 Safety Review**

Investigators and the DSMB may recommend discontinuation of any of the treatment arms for safety reasons or a very low probability of successfully addressing the study hypotheses within a feasible time frame, because of inadequate recruitment, compliance, drug response, effect size of outcome, etc. This discontinuation may apply to one or all sites. All votes will be decided by a simple majority. The NIAID will make the final decision on whether or not to accept the DSMB's recommendation to discontinue any component of the study.

### **11.12 Immunogenicity or Efficacy Review**

Since this is a Phase III trial of medications that are being used for their intended use, there should be no need to conduct interim analyses.

### **11.13 Final Analysis Plan**

Analyses will be conducted in an intent-to-treat manner with variables categorized per protocol. To assure that randomization has been achieved, selected demographic, clinical and behavioral (including medication adherence and sexual re-exposure) factors will be compared by study arms using chi-square, t-test or ANOVA, where applicable. If randomization was found to be successful (as indicated by even distribution of potential confounders) then analyses will be conducted with no need to adjust for confounding. If randomization was not achieved, then associations will be explored for potential confounding and if found these factors will also be included in the model. From the two aims, there are two hypotheses:

H1: Women receiving multi-day MTZ will be less likely to test TV positive at TOC compared to women who receive the single dose MTZ.

H2: This effect (H1) will only be observed among women who have BV (Nugent score  $\geq 7$ ).

Analysis: The research questions will be answered using a multivariable logistic regression analysis to examine the effect of single versus multi-dose (H1) and the differential impact of BV on this effect (H2). This primary logistic model contains two main effects (i.e. treatment and BV)

Version: 11.0

[figure not shown]
Version date: 1/2/17

and 1 first order interaction (BV by index treatment)). The model (1) will be:  $g(Y_i) = \beta_0 + \beta_1 + \beta_2 + \beta_1 \cdot \beta_2$  where:  $g(Y_i) = \log$  odds of repeat infection,  $\beta_0 =$  coefficient for the intercept,  $\beta_1 =$  (Factor 1) single versus multi-dose,  $\beta_2 =$  (Factor 2) BV at time of visit

All analyses will be conducted in SAS by Tulane staff under the direction of [name]. Because we will use strict protocols and employ tight supervision of the study sites and the study populations are similar (mostly African American and underserved) we do not anticipate site variations but we will examine for any differences and if found, we will include a site variable in the models. We do not anticipate a three-way interaction, and our simulations (see below) support that belief. We will, however, run a fully parameterized model including all main effects, first order interactions, and second order interaction before running the primary analysis model (1) above. We will consider any p-value less than 0.05 to be significant and any p-value less than 0.10 as near-significant. If there is unexpected significant or near-significant interaction, we will stratify on BV status and assess the impact of index treatment (single vs. multi-dose) and any possible interaction separately for BV positive and BV negative women.

Additional analyses– The ACASI will allow for examination of index adherence to medication, index knowledge of partner treatment, sexual exposure and the nature of the sexual act and sexual partner, condom use. These factors will be assessed by arm to determine if any confounding occurred and if so, these analyses will be adjusted for these factors or stratified by these factors.

**Figure 4:** Algorithm for determining origin of repeat infection at TOC

**Outcome measures** – The study is powered for repeat infections. Since we will have information on sexual exposure and genotyping, we can also refine this outcome measure to examine treatment failure (H1 & H2) and reinfection and will use the algorithm depicted in figure 4.

All analyses will be conducted in SAS by the Tulane staff under the direction of [name]. As the data collection instruments are designed to

minimize missing data we do not anticipate an excessive amount. However, imputation techniques will be utilized to compensate for missing data (e.g. multiple imputation and maximum likelihood). Sensitivity analyses will be conducted to ensure that the method chosen to account for missing data does not bias the study’s results. Additionally, the characteristics of those who complete the study will be compared to those who drop out to determine whether drop out is informative. If not, multiple imputation methods will be used for initial analyses. If,

instead, data are non-ignorably missing, weighted regression methods will be explored but extreme caution will be used in interpreting results. Regardless of missingness mechanism, complete case analysis will also be performed for comparison.

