### **6.2 Assessment of Participant Compliance with Study Agent(s)/Intervention(s)**

Participants randomized to the single dose of MTZ will be asked to take their medication at the clinic under direct observation. If there are any complications taking the medication, it will be noted on her study folder.

Those randomized in the 7 day arm will be asked to take their first dose under direct observation at the clinic and instructed to take the additional doses over the following six days.

At the follow up visits, participants will be asked to report adherence to medication on their ACASI surveys.

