## **11.5 Appropriate Methods and Timing for Analyzing Outcome Measures.**

The primary outcome measure is TV infection. All women will be TV positive at baseline and will be screened for TV using InPouch culture and NAAT at follow up visits. Binary (TV positive or TV negative)

Key secondary outcomes are:

Version: 11.0

Version date: 1/2/17

BV which will be measured by self-collected vaginal swabs and Gram stain screening at all visits. Categorical (Scores of 7 -10 are considered to indicate BV). This measure will add information about the primary outcome measure by indicating whether BV affects TV repeat infections.

Re-exposure, which will be self-report by the participant for each partner. This data will be collected on the behavioral survey at follow up visits. Binary (partner treated and /or no sexual exposure prior to screening vs. partner not treated and sexual exposure prior to screening, This measure will allow us to adjust for the confounding effects of sexual exposure/re-exposure.

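### Section 11.13 lets adherence and sexual re-exposure, both measured after randomization, enter the H1/H2 model, so the reported arm effect may not be the intent-to-treat effect

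*Combined protocol and SAP*

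**What the plan says.** Section 11.13 opens by committing to intent-to-treat. It then sets a two-step rule. First, as a check on randomization, "selected demographic, clinical and behavioral (including medication adherence and sexual re-exposure) factors will be compared by study arms", and an even distribution is taken to mean success. Second, "If randomization was not achieved, then associations will be explored for potential confounding and if found these factors will also be included" in the model. The two hypotheses and the model follow directly: "This primary logistic model contains two main effects (i.e. treatment and BV") and their interaction. A fuller model with higher-order interactions is to be run "before running the primary analysis model (1) above".

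On timing, section 11.8 says "Randomization will occur at the end of each baseline study visit". Section 6.2 says of adherence: "At the follow up visits, participants will be asked to report adherence to medication on their ACASI surveys". Section 11.5 lists re-exposure among the key secondary outcomes and says of it "This data will be collected on the behavioral survey at follow up visits" and "This measure will allow us to adjust for the confounding effects of sexual exposure/re-exposure". Section 14.7 describes adherence as an outcome of the study.

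**The concern.** Randomization can be checked only against variables fixed before it took place. Adherence and re-exposure arise afterwards and may be consequences of the assigned regimen. An arm difference in either is no evidence that randomization failed.

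The second step does not screen them out. A post-randomization variable related to both arm and outcome looks exactly like a confounder in the data. Once it is in the model, women are still classified by assigned arm, but the arm coefficient is conditional on adherence or re-exposure. It no longer estimates the effect of assignment, and which of the two effects is reported depends on the data.

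For adherence the trigger is close to built in. Section 8.2 has the whole single dose taken under observation, but only the first of 2 × 7 = 14 doses in the 7-day arm, and section 2.1 says single dosing took adherence away as an issue. If non-adherent women fail more often, adjustment removes the cost of incomplete courses and makes the 7-day regimen look better than it is as assigned. For re-exposure only the timing is documented, so the direction of any shift is unknown.

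**Working it through.** **Inputs from the documents.** Section 11.7: failure 16.2% (single dose) and 10.7% (7-day), power 0.80, base N 1206, 1332 evaluable, so 1332/2 = 666 per arm. Section 11.13: p < 0.05 as the general significance level, with no threshold set for the balance check or for finding confounding.

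**The plan's own figure.** Two proportions, pooled variance, two-sided 0.05: n = [1.960·√(2 × 0.1345 × 0.8655) + 0.842·√(0.162 × 0.838 + 0.107 × 0.893)]² / 0.055² ≈ 603 per arm, or 1206. It reproduces, and it rests on the unadjusted contrast, whose odds ratio is (0.107/0.893)/(0.162/0.838) = 0.620.

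**Assumed inputs (not in the documents).** Single-dose adherence 99%; 7-day adherence 80–95%; failure 1.5–3 times as frequent in non-adherent women; p < 0.05 at both steps; BV prevalence 60% in both arms, independent of adherence.

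**Step 1, the balance check.** At 666 per arm, a p < 0.05 test flags 99% v 97% adherence with probability 0.74 and 99% v 95% with probability 0.99, although randomization is sound.

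**Effect of adjustment.** Hold each arm's overall failure rate p fixed. With adherent share a and failure ratio k, failure in adherent women is p/(a + (1 − a)k), and in non-adherent women k times that. At 85% and k = 2:

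- 7-day: 0.107/1.15 = 9.30% adherent, 18.61% non-adherent.
- Single dose: 0.162/1.01 = 16.04% adherent, 32.08% non-adherent.
- Odds ratios within strata: 0.537 (adherent) and 0.484 (non-adherent). The logistic model with arm and adherence gives 0.535.
- With 16.2% in both arms, the true odds ratio of 1 becomes 0.857.

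**False-positive rate of the two-step rule.** Simulation under 16.2% v 16.2%, 6000 runs per setting. Adherence enters if it is uneven by arm and related to outcome, each at p < 0.05. Ranges cover a crude or arm-adjusted second step and a BV failure ratio of 1 or 2. Coding matters because with BV coded 0/1 the arm coefficient is the effect in BV-negative women; the plan does not state the coding.

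| 7-day adherence / failure ratio | Adjusted OR, design (0.620 unadjusted) | Adjusted OR, null (1 unadjusted) | False positives, no BV term or BV centred | False positives, BV coded 0/1 |
|---|---|---|---|---|
| 95% / 1.5 | 0.606 | 0.977 | 4.9–5.4% | 4.9–5.1% |
| 95% / 2 | 0.592 | 0.955 | 5.8–6.3% | 5.1–5.6% |
| 90% / 1.5 | 0.590 | 0.949 | 4.8–6.4% | 4.7–5.1% |
| 90% / 2 | 0.562 | 0.903 | 9.3–9.9% | 6.1–7.3% |
| 85% / 2 | 0.535 | 0.857 | 14.7–16.4% | 8.8–9.5% |
| 80% / 3 | 0.431 | 0.688 | 60.2–61.7% | 28.3–31.2% |

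Without the rule the rate is 4.3–5.5% throughout. At 85% / 2, adherence passes the second step in 91–93% of null trials and 46–79% of trials at the design rates. If adherence has no relation to failure (ratio 1), the odds ratio stays at 0.620.

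**Re-exposure (assumed shares, threefold failure).** At 20% single dose v 15% 7-day, failure in women not re-exposed is 0.162/1.4 = 11.57% v 0.107/1.3 = 8.23%, odds ratio 0.685; in re-exposed women it is 34.71% v 24.69%, odds ratio 0.617. The logistic model gives 0.662, and 1.10 under the null. With the shares reversed it gives 0.552. The shift can go either way.

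**The case against.** The best counter-argument is about scope. Model (1), the only analysis called primary, contains just treatment, BV and their interaction, and section 11.3 describes a plain comparison of arms. Later in 11.13 the survey-based factors fall under additional analyses, and the Protocol Summary and sections 3.3 and 4.2.3 treat them as exploratory. On that reading the adjusted models are already supplementary. But those labels do not reach the randomization-check rule, which names adherence and re-exposure, says they will enter the model, and stands immediately before H1, H2 and model (1). Nothing limits adjustment to baseline variables or keeps an unadjusted contrast primary once imbalance is found.

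The objections on size largely stand. No adherence rate is documented, section 14.7 makes observed dosing preferred but not mandatory, and section 8.2 gives the 7-day arm extra adherence counselling. Adherence above 95% or a ratio near 1.5 leaves the error rate close to nominal, and the 60% figure needs both extremes together. These are also false positives only with respect to the effect of assignment: in the 85% / 2 null, failure among adherent women truly differs (14.1% v 16.0%). That is a different question from the one intent-to-treat answers.

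Two further points are fair. Only adherence has a documented mechanism; both arms receive the same advice on sex and partners. And the BV-by-arm interaction already makes the arm coefficient in model (1) specific to a BV level. That is a separate matter and does not rescue the rule.

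**Conclusion.** The rule is wrong as written and must be changed. The case rests on the text: two variables measured after randomization are used to judge it, and they can enter the model for the primary hypotheses under an intent-to-treat heading. This conclusion needs no assumed rates.

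The size does need them. It ranges from negligible (95% adherence, failure ratio 1.5) to serious (80%, ratio 3), with a middle case of 85% and ratio 2 in which the null odds ratio drifts to 0.857. If non-adherent women fail more often, the bias favours the regimen hypothesized to be superior, in a trial meant to inform treatment recommendations. For re-exposure neither size nor direction can be fixed from the documents. The sample size is unaffected.

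**What to change.** - In 11.13, restrict the balance check, and any covariate added to model (1) for H1 or H2, to variables measured before randomization.
- In 11.13, state that the as-randomized contrast without post-randomization covariates stays primary whatever the balance check shows.
- In 11.13 and 11.5, state that adherence, re-exposure, partner treatment and condom use are described by arm, and that analyses adjusted for or stratified by them are supplementary.
- Bring the matching adjustment sentences in the Protocol Summary, 3.3 and 4.2.3 into line, so that the protocol does not contradict itself.

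The timing of the BV term already in model (1) should be settled separately.

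The cost is a wording amendment, with DSMB approval if the change is judged significant (10.2.1) and reporting to the IRB (9.9). It needs no new data and leaves 1206 and 1664 as they are. The adjusted analyses can still be run under their supplementary label.

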**Aim 2: Host factors - To determine if altered vaginal flora, as measured by Nugent score, interferes with TV treatment.**

These aims will be accomplished by conducting a phase III randomized clinical trial among TV infected HIV negative women (N=1664) attending clinics in New Orleans, LA, Birmingham, AL or Jackson, MS. These public clinics serve mostly African American, low income women, the demographic group most highly affected by TV. Women will be randomized to a single dose or multi-dose arm. Test of cure will be conducted at 4 weeks post treatment completion. Viable vaginal specimens from women who are TV+ at TOC will undergo MTZ susceptibility testing and TV genotyping (to compare baseline and follow-up types). Self-collected specimens from women who provide specific consent will be stored for future microbiome studies of the vaginal flora and other related studies. The information obtained from this study will be used to refine treatment recommendations and to better understand the origins of repeat TV infections. Given the strong multi-centered, RCT design, and the large sample size, results should rapidly inform treatment guidelines thus having high impact.

***The ultimate goal is improved reproductive health for women, particularly minority women, and the reduction of the potential for HIV transmission, fitting well with NIAID's mission.***

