## 6.1 Study Agent Acquisition

### 6.1.1 STUDY AGENT/INTERVENTION # 1 -- Metronidazole

#### 6.1.1.1 Formulation, Packaging, and Labeling

Generic MTZ will be provided on site at all clinics. Treatment will be given by the study provider (RN, NP, MD). Medication that is not consumed in the clinic will be in containers with child-proof caps, labeled with dose, instructions, and contact information for the clinic and the study personnel. Also warning labels will be on the container (for multi-dose) which will instruct users to refrain from alcohol consumption and to not take if there are known allergies to MTZ.

Subjects receiving the single dose will be provided the information verbally. Participant dose will be determined at randomization. Half of the women (n=832) will be randomized to receive the single dose and the other half (n=832) will be randomized to receive the 7 day dose.

MTZ 2 g single oral dose - (CDC recommended treatment regimen) Following randomization, women assigned to the single dose arm will be given the 2 g oral dose of MTZ under direct observation. If for any reason a participant is unable to take the medication DOT, this will be recorded in their study chart and adherence questions will be asked at the follow up visit.

MTZ 500 mg oral dose BID for 7 days - (CDC alternative treatment regimen) Following randomization, women assigned to the 7 day arm will be given the 500 mg oral dose BID for 7 days with the first dose given under direct observation. If for any reason a participant is unable to take the first dose DOT, this will be recorded in their study chart and adherence questions will be asked at the follow up visit.

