### **8.2 Enrollment/Baseline**

The study will be described to potential participants by study staff and any questions will be answered and documented in the study records. Each site has an eligibility checklist for the study staff to use to confirm eligibility. As part of her eligibility checklist, staff will determine if a potential participant was given a pregnancy test at her clinical visit and confirm that the test was negative or that she had a hysterectomy or is post-menopausal for at least two years. If the woman is willing to participate and is eligible for the study, staff will obtain informed

Version: 11.0

Version date: 1/2/17

consent and provide a copy to participant. After consent is obtained, if a woman did not provide a urine pregnancy test as part of her clinical visit or meet the other criteria to determine she was not pregnant, she will be asked to provide a urine sample for testing. If the test is positive, women will be told that she is ineligible to continue with the study protocol since pregnancy is an ineligibility criterion. Study staff will provide her with her baseline compensation and refer her for pregnancy counseling as per each clinic's standard of care. The participant will be withdrawn prior to randomization and her randomization number will be used for the next participant. A participant may also be withdrawn from the study prior to randomization if she is found to meet other ineligibility criteria post-consent and pre-randomization. In these cases, she would receive her compensation and her randomization number would be used for the next participant.

If the participant is negative for pregnancy, she will undergo the audio computer assisted self-interview (ACASI). This survey will take approximately 30-45 minutes to complete and will be conducted after the clinical exam and written informed consent is obtained but before randomization to treatment. Information elicited will include detailed information about participants' demographics, socioeconomics, STI risk behavior and symptoms, substance use, and birth control methods, as well as partner specific information about sexual behavior, condom usage, and partnership status.

Women will be asked to self-collect vaginal swabs for Gram stain testing, In Pouch, TV NAAT and FMS. The participant will be given three or four sterile swabs and tubes and instructed on how to self-swab, place the swab in the tubes and return to the study office.

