## 11.6 Study Hypotheses

From the two aims, there are two hypotheses:

H1: Multi-dose (alternate) MTZ is superior to the single dose (recommended) for the treatment of TV among HIV-negative women.

H2: Altered vaginal flora (measured by Nugent's score) interferes with the MTZ treatment of TV for the single dose but not the multi-dose.

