## 11.7 Sample Size

### Considerations

[figure not shown]
This RCT will allow for evaluation of index dosing of MTZ by BV status. This study examines two hypotheses simultaneously:

H1: Women receiving multi-day MTZ will be less likely to test TV positive at TOC compared to women who receive the single dose MTZ.

H2: This effect (H1) will only be observed among women who have BV (Nugent score  $\geq 7$ ).

From our pilot work, we found the rates of repeat infection at TOC to be 16.2% for single dose and 10.7% for multi dose at a power of 0.80, we will need 1206 subjects. If we account for a 5% Inner Class Correlation (ICC) for correlation of the subjects within the 4 sites using the formula  $1=(M-1)*ICC$ . We will need to inflate by 15%. We will also inflate by 20% to accommodate for our anticipated follow-up for a required sample size of 1664. We will have 1332 evaluable unites at TOC, which will provide adequate power taking into consideration the ICC.

Figure 1.  
Randomization Scheme

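### Section 11.13 lets balance by treatment arm settle adjustment for the BV question too, but BV is not randomized, so the Aim 2 conclusion that flora interferes with treatment is open to confounding

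*Combined protocol and SAP*

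**What the plan says.** Only treatment arm is randomized, in blocks within site (section 11.4). BV is a Nugent-score characteristic that the woman brings to the trial.

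Section 11.13 sets one check and one rule. For the check, selected demographic, clinical and behavioral "factors will be compared by study arms using chi-square, t-test or ANOVA, where applicable". The rule for a favorable result is "as indicated by even distribution of potential confounders) then analyses will be conducted with no need to adjust for confounding". The model that follows contains treatment, BV and their product, with no covariates, and serves both hypotheses. Sections 3.3, 4.2.3 and 11.13 put the survey factors (adherence, partner treatment, sexual exposure, condom use) through the same by-arm check.

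H2 appears in two forms:

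- In sections 3.1, 11.7 and 11.13, the dose effect is expected only in women with BV. This is effect modification.
- In sections 11.1 and 11.6, altered flora "interferes with the MTZ treatment of TV for the single dose but not the multi-dose". Aim 2 in section 2.1 reads "To determine if altered vaginal flora, as measured by Nugent score, interferes with TV treatment". This is a causal statement about BV.

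No section compares factors by BV status or names covariates for the BV terms.

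**The concern.** Randomization makes the arms comparable. It does nothing to make women with BV comparable to women without it. A factor can be evenly spread across the arms and still be much commoner among BV-positive women. If it also raises the chance of a positive test of cure, it produces a BV contrast that BV did not cause. The primary endpoint is any positive result at test of cure and so includes reinfection, which makes partner and sexual-risk factors plausible candidates. The baseline survey records such factors before randomization: "STI risk behavior and symptoms, substance use, and birth control methods, as well as partner specific information about sexual behavior".

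For the Aim 2 question, then, the by-arm check tests the wrong contrast. A well-randomized trial would pass it, fit the model unadjusted, and could report that flora interferes with the single dose when something that travels with BV is responsible. BV's role is half of the primary objective, and section 4.1 expects the results to inform treatment guidelines rapidly.

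**Working it through.** **The plan's own sample size.** Section 11.7 gives "16.2% for single dose and 10.7% for multi dose at a power of 0.80, we will need 1206 subjects". Alpha is not stated there; section 11.13 says "We will consider any p-value less than 0.05 to be significant", and I take it as two-sided. Allocation is 1:1 (section 6.1.1.1: "Half of the women (n=832) will be randomized to receive the single dose"). With pooled variance and mean rate 0.1345:

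n per arm = [1.96·√(2·0.1345·0.8655) + 0.8416·√(0.162·0.838 + 0.107·0.893)]² / 0.055² = (0.9457 + 0.4048)² / 0.003025 ≈ 603, so 1206 in total.

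Then 1206 × 1.15 × 1.20 = 1664.3, matching 1664. This sizing concerns the dose comparison only. The 1332 evaluable women give 666 per arm.

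**Would the by-arm check catch the problem?** No. For a factor present in 50% of BV-positive and 20% of BV-negative women (61% with BV), equally common in both arms, 20,000 simulated trials flagged an arm imbalance in 5.1%. That is the nominal rate.

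**Size of the spurious BV effect.** Assumptions, since the documents give no confounder strengths:

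- BV has no effect.
- 155/230 = 67.4% of women have BV. This is borrowed from Table 4, which describes HIV-positive women; this trial enrolls HIV-negative women.
- Arm rates are 16.2% and 10.7%.
- The factor has prevalence z1 in BV-positive and z0 in BV-negative women and multiplies risk by k.

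Spurious RR = (z1·k + 1 − z1) / (z0·k + 1 − z0). At 50% vs 30%:

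- k=2: 1.5/1.3 = 1.15
- k=3: 2.0/1.6 = 1.25
- k=4: 2.5/1.9 = 1.32

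For k=4 the single-dose rates are 17.6% with BV and 13.4% without. With 449 and 217 women, SE = √[0.162·0.838·(1/449 + 1/217)] = 0.0305. The chance of a significant false BV harm is about Φ(0.0422/0.0305 − 1.96) ≈ 28%, against a nominal 2.5%.

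Simulation (40,000 trials per row):

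| Factor prevalence, BV+ vs BV− | k | Spurious RR, single dose | False BV harm, within-arm test | BV-by-treatment test, factor acts equally in both arms | Same test, factor acts only under single dose |
|---|---|---|---|---|---|
| 50% vs 30% | 2 | 1.15 | 10% | 5% | 8% |
| 50% vs 30% | 3 | 1.25 | 20% | 5% | 12% |
| 50% vs 30% | 4 | 1.32 | 28% | 5% | 15% |
| 60% vs 30% | 4 | 1.47 | 48% | 5% | 25% |

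In the last column the dose effect really does differ between BV groups, because the factor differs between them. As a test of effect modification, the rejection is correct. What would be wrong is attributing it to BV.

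**Events available for adjustment.** 666 × 0.162 + 666 × 0.107 = 107.9 + 71.3 ≈ 179 in total. Among 7-day women without BV there are about 666 × 0.326 × 0.107 ≈ 23.

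**The case against.** The strongest reply is that section 11.13 tests H2 through the BV-by-treatment term and, if there is interaction, compares arms within BV strata. Randomization protects those comparisons when BV is taken at baseline. No section plans a BV-positive versus BV-negative test within each arm, or attaches a decision rule to one. This stands. A reader might infer that H2 has a false-positive rate of 10% to 28%, but the documents do not support that: those figures belong to a within-arm BV contrast, which is the form of the pilot evidence in Table 4 (RR 4.16 single dose, 1.07 for 7 days) but not of the planned test.

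A reader might also infer that the plan bars all adjustment. It does not. Saying there is no need to adjust is not a prohibition. Section 11.13 adds a site term if sites differ, and section 11.5 says the re-exposure measure will permit adjustment. Neither closes the gap: 11.13 does not carry re-exposure into the model, re-exposure is measured after randomization, and neither item compares BV groups on baseline factors.

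Finally, sections 4.2.2 and 11.13 refine the outcome to treatment failure for both hypotheses, using sexual history and genotype. This addresses part of the reinfection route, but it is secondary and supplies no covariates for BV.

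None of this supports the causal wording. An effect-modification test shows that the dose effect differs between BV groups, not that BV is the reason.

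**Conclusion.** The point holds for the BV term and for the Aim 2 conclusion that altered flora interferes with single-dose treatment. It does not touch H1, or the arm effects within baseline-BV strata. Section 11.13 labels the BV factor as BV at the time of visit, so the within-stratum protection depends on reading that as the baseline visit.

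Under the assumed strengths (50% vs 30%, multiplier 2 to 4) the spurious single-dose BV risk ratio is 1.15 to 1.32, and a within-arm test shows false BV harm in about 10% to 28% of trials. The planned interaction test stays at about 5% if the factor acts equally in both arms. If it acts only under single dose, the test rejects in about 8% to 15%, or 25% at 60% vs 30% with a multiplier of 4. These sizes rest on assumed confounder strengths and on a BV prevalence borrowed from HIV-positive women. The logical gap does not depend on them. This should be fixed, but it does not threaten the trial's main comparison.

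**What to change.** In section 11.13:

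1. Limit the no-adjustment sentence to the arm comparison: H1, and arm effects within strata of baseline BV.
2. Tabulate baseline factors by baseline BV status as well as by arm.
3. Pre-specify one H2 sensitivity model with a short list of reliably collected pre-randomization covariates: site, age, and one or two baseline survey items on partners or sexual risk. Add their products with arm only where events allow. Report the BV and BV-by-treatment terms with and without adjustment. Co-occurring STI is a poor candidate, because section 6.3 records it only when available.
4. In Aim 2 and sections 11.1 and 11.6, word the conclusion as effect modification by, or association with, baseline BV. Adjustment would not by itself justify the word interference, because residual confounding remains.

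The cost is wording, one table and one extra model with a few parameters, on data already collected. With about 179 expected events the covariate list must stay short. It should be fixed before outcomes by arm are seen, because covariates chosen afterwards would carry much less weight.
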